8.2.3. Deaths and Serious Adverse Events

Total number of serious adverse events as well as the number and percentage of subjects reporting at least one serious AE will be provided for each treatment group. Total number of serious adverse events as well as the number and percentage of subjects reporting each serious AE will be reported by treatment group, primary system organ class and preferred term. On-treatment and post-treatment serious AEs will be summarized separately, as well as together as post-randomization serious AEs. A summary of post-randomization serious AEs will be provided by treatment group and time period (Months 1-6, Months 7-12, Months 13-18, Months 19-24), by treatment group and age group (<65 years, \geq 65 years), by treatment group and age group (<75 years, \geq 75 years), and by treatment group and country. A summary of all post-randomization drug-related serious AEs, of all post-randomization fatal AEs, and of all post-randomization drug-related fatal AEs will be provided by treatment group. Time to death will be summarized by treatment group using Kaplan-Meier estimates and displayed as Kaplan-Meier plots.

Individual subject listings of all non-fatal serious AEs and a separate listing of all fatal serious AEs will be provided. The listing will indicate the timing of the serious AE with respect to treatment start date.

8.2.4. Adverse Events Leading to Discontinuation of Investigational Product and/or Withdrawal From the Study and Other Significant Adverse Events

8.2.4.1. Adverse Events Leading to Discontinuation of Investigational Product and/or Withdrawal from the Study

A summary of adverse events starting post-randomization and leading to withdrawal from the study will be provided by treatment group for the following categories:

- All AEs
- Drug-related AEs
- Serious AEs

Similar summaries will be provided for adverse events leading to permanent discontinuation of the study medication.

Subject listings of AEs leading to withdrawal from the study and AEs leading to permanent discontinuation of study drug will be provided. The listings will indicate the timing of the AE with respect to treatment start date.

8.2.4.2. Adverse Events of Special Interest

Tier 1 adverse events of special interest are pre-specified adverse event preferred terms for which there are predefined hypotheses about the existence of a potential treatment effect. These events include the following:

- Sexual and breast events
- Prostate cancer
- Cardiovascular events
- Infrequent events

Summaries for these events are specified in the following sections and will be based on post-randomization AEs unless otherwise indicated. A mapping of the MedDRA primary system organ class and preferred term to which each verbatim term in the special interest AE categories has been coded will be provided in a listing.

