The most common AEs (Tier 2 events) are defined as those preferred terms occurring in at least 5% of the subjects within any treatment group (non-rounded). The total number of events as well as the number and percentage of subjects reporting at least one most common AE preferred term starting post-randomization will be provided for each treatment group. The number of events, the number and percentage of subjects reporting the most common AE preferred terms starting post-randomization will be provided by treatment group displayed by decreasing frequency of preferred terms (regardless of primary system organ class). For each of these most common AEs, the percentage of subjects in the treatment groups will be compared using Fisher's exact test. In addition, the percentage of subjects reporting each AE by treatment group along with the corresponding odds ratio and 95% confidence interval for each of the most common AEs

will be displayed in a figure sorted by odds ratio in descending order, by treatment group. The above summary will also be provided for the most common non-serious post-randomization AEs.

Total number of drug-related adverse events as well as the number and percentage of subjects reporting at least one drug-related AE will be provided for each treatment group. Total number of drug-related adverse events as well as the number and percentage of subjects reporting each drug-related AE will be reported by treatment group, primary system organ class and preferred term. On-treatment and post-treatment drug-related AEs will be summarized separately, as well as together as post-randomization drug-related AEs. A summary of post-randomization drug-related AEs will be provided by treatment group and time period (Months 1-6, Months 7-12, Months 13-18, Months 19-24), by treatment group and age group (<65 years, \geq 65 years), by treatment group and age group (<75 years, \geq 75 years) and by treatment group and country.

A listing of all AEs, a listing of AEs by onset period, and a listing of which subjects reported specific AEs will be presented. A listing of Possible Suicidality Related Adverse Event (PSRAE) data will be provided. A listing of the sexual function Targeted Follow-Up Questionnaire (TFUQ) data will be provided.

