8.2.4.3. Sexual and Breast Tier 1 Adverse Events of Special Interest

Altered (decreased) libido, impotence, ejaculation disorders, and breast disorders, will be defined as sexual and breast adverse events of special interest. In addition, two subgroups of breast disorders (breast disorders: breast enlargement, and breast disorders: breast tenderness) are of special interest. MedDRA system organ class and preferred terms included in these special interest adverse events are defined in [Appendix 8, Table A](#).

Total number of, as well as number and percentage of the subjects experiencing, sexual and breast adverse events of special interest will be provided by treatment group. In addition, for each of the events of special interest, the number and percentage of subjects by treatment will be provided for the following:

- having an event
- having multiple events
- having an event in 6-month windows, starting from treatment start date

The following categories are related to the occurrence of the first event of the special interest AE; number and percentage of subjects in these categories will be provided by treatment group:

- drug-related AE
- serious AE
- AE leading to withdrawal from the study
- AE leading to permanent discontinuation of study drug
- AE outcome
- AE resolution status (on-therapy vs. off-therapy – see [Appendix 8](#) for definition)
- AE maximum intensity

The number and percentage of the subjects experiencing an adverse event of special interest will be provided by treatment group for the following. The by-baseline summaries will be output in the above described overall tabular summaries:

- By baseline age group: < 65 years, ≥65 years
- By sexual activity at baseline (Yes, No) based on “sexually active” question.

The number and percentage of subjects experiencing the following types of sexual and breast adverse events of special interest will be provided by treatment group:

- Any Type (Impotence, Decreased Libido, Ejaculation Disorders, or Breast Disorders)
- One AE Type
- Two AE Types
- Three AE Types
- All Four AE Types

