The time to first onset in days will be summarized by treatment group as a continuous variable as well as by time period of onset. In addition, time to first adverse event of special interest will be summarized by treatment group using estimates calculated by the Kaplan-Meier method and displayed graphically as Kaplan-Meier curves. Time to resolution for the first event in days will be summarized by treatment group.

Duration of adverse events of special interest will be summarized by treatment group for uncensored values, censored values, and all values. It is recognized that summary statistics such as means and medians involving censored values will be biased (low).

The number of sexual and breast adverse events leading to study withdrawal, as well as the number and percentage of subjects reporting at least one such sexual and breast adverse event will be provided for all event types and also by event type for each treatment group.

Resolution status at end of study (resolved, not resolved) and time from treatment stop date to AE resolution will be summarized by treatment group for the sexual and breast adverse events leading to study withdrawal and not resolved at Month 24 / End of Treatment visit.

Listings of sexual and breast adverse events of special interest will be provided. A listing of sexual and breast adverse event status data will be provided.

A listing of the TFUQ data for sexual and breast adverse events will be provided.

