8.2.4.5. Cardiovascular Tier 1 Adverse Events of Special Interest

Cardiovascular adverse events of special interest will be defined as those included in the following six categories: acute coronary syndrome, ischemic coronary artery disorders/atherosclerosis, ischemic cerebrovascular events, cardiac failure, cardiac arrhythmias, and peripheral vascular disease. MedDRA preferred terms and codes included in these special interest adverse events are defined in [Appendix 8, Table C](#). Total number of cardiovascular events as well as the number and percentage of subjects experiencing cardiovascular events will be provided by treatment group. Each category of cardiovascular events, and all cardiovascular events as one additional category, will be summarized separately following the same format done for sexual and breast special interest AEs described above. Time to first cardiovascular adverse event of special interest will be summarized by treatment group using estimates calculated by the Kaplan-Meier method and displayed graphically as Kaplan-Meier curves.

Listings of cardiovascular adverse events of special interest will be provided.

Note: The protocol Section 7.4.2.2 (Cardiovascular Events) indicates additional data collection required for some cardiovascular events and procedures; these data will be output in data listings. Cardiovascular events in protocol Section 7.4.2.2 are not the full set of cardiovascular adverse events defined in this RAP section.

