11.15.6. Safety Figures

3.1	Plot of Study Drug Exposure
3.2	Plot of Power to Detect a Difference in Adverse Event Rate for Combination versus Tamsulosin
3.3	Most Common Adverse Events Starting Post-Randomization, Sorted by Odds Ratio
3.4	Plot of Kaplan-Meier Estimates of Time to First Altered (Decreased) Libido Adverse Event
3.5	Plot of Kaplan-Meier Estimates of Time to First Impotence Adverse Event
3.6	Plot of Kaplan-Meier Estimates of Time to First Ejaculation Disorder Adverse Event
3.7	Plot of Kaplan-Meier Estimates of Time to First Breast Disorder Adverse Event
3.8	Plot of Kaplan-Meier Estimates of Time to First Breast Disorder: Breast Enlargement Adverse Event
3.9	Plot of Kaplan-Meier Estimates of Time to First Breast Disorder: Breast Tenderness Adverse Event
3.10	Plot of Kaplan-Meier Estimates of Time to First Prostate Cancer Adverse Event
3.11	Plot of Kaplan-Meier Estimates of Time to First Acute Coronary Syndrome Adverse Event
3.12	Plot of Kaplan-Meier Estimates of Time to First Ischemic Cerebrovascular Adverse Event
3.13	Plot of Kaplan-Meier Estimates of Time to First Cardiac Failure Adverse Event
3.14	Plot of Kaplan-Meier Estimates of Time to First Ischemic CAD/Atherosclerosis Adverse Event
3.15	Plot of Kaplan-Meier Estimates of Time to First Cardiac Arrhythmia Adverse Event
3.16	Plot of Kaplan-Meier Estimates of Time to First Peripheral Vascular Disease Adverse Event
3.17	Plot of Kaplan-Meier Estimates of Time to First Cardiovascular Adverse Event
3.18	Plot of Kaplan-Meier Estimates of Time to Death

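### Pooled Tier 1 safety categories, defined by predefined treatment-effect hypotheses, have no between-arm estimate, interval or test specified in the RAP text, although frequency-selected Tier 2 terms do

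*SAP*

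**What the plan says.** **Tier 1.** Section 8.2.4.2 defines these as "pre-specified adverse event preferred terms for which there are predefined hypotheses about the existence of a potential treatment effect" and names four groups: sexual and breast events, prostate cancer, cardiovascular events and infrequent events. It says the summaries are those set out in the sections that follow.

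- Sexual and breast (8.2.4.3): "number and percentage of the subjects experiencing, sexual and breast adverse events of special interest will be provided by treatment group". Onset, resolution and duration are also summarised by arm, and "time to first adverse event of special interest will be summarized by treatment group using estimates calculated by the Kaplan-Meier method".
- Prostate cancer (8.2.4.4): the same format.
- Cardiovascular (8.2.4.5): "Total number of cardiovascular events as well as the number and percentage of subjects experiencing cardiovascular events will be provided by treatment group". Six categories, and all of them combined, follow the same format.
- Infrequent events (8.2.4.6): counts and percentages by arm.

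**Tier 2.** Section 8.2.2 defines these as "preferred terms occurring in at least 5% of the subjects within any treatment group" and specifies a test: "For each of these most common AEs, the percentage of subjects in the treatment groups will be compared using Fisher's exact test". It also specifies a figure showing the "corresponding odds ratio and 95% confidence interval for each of the most common AEs". Section 11.15.6 lists it as Figure 3.3, "Most Common Adverse Events Starting Post-Randomization, Sorted by Odds Ratio".

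**The concern.** A predefined hypothesis about a treatment effect calls for at least an estimate of that effect and its uncertainty. The plan gives both to terms that enter by observed frequency, and neither to the categories that it says carry a hypothesis.

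Tier 2 works on single preferred terms, whereas most Tier 1 categories pool several. A pooled category can therefore be common while none of its terms reaches 5%. A rare category will probably never enter Tier 2. For rare events the most useful result is the upper limit of the excess that the data still allow, and that limit is not specified.

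**Working it through.** The main check is textual. The arithmetic only illustrates it.

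**1. Search for any Tier 1 comparison.** Sections 8.2.4.2 to 8.2.4.6, Appendix 8, Appendix 11, the titles of Tables 3.41 to 3.63 and the titles of Figures 3.4 to 3.17 name no risk difference, odds ratio, hazard ratio, log rank test or Fisher test for a Tier 1 category.

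**2. Is this a declared descriptive policy?** Elsewhere the plan says so when no comparison is intended: for the supporting IPSS summaries in 7.1.3 and the other efficacy measures in 8.1.6. The Tier 1 sections carry no such statement. Safety comparisons are otherwise routine:

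| Section | Data | Comparison |
|---|---|---|
| 8.2.2 | Six overall AE sets | Fisher |
| 8.2.2 | Tier 2 terms | Fisher, odds ratio with 95% interval |
| 8.2.7 | PSA change | General linear model |
| 8.2.8 | Post-void residual volume change | van Elteren |
| 8.2.9 | Breast examination shifts | Fisher |
| 8.2.10 | Rectal examination shifts | Fisher |
| 8.2.11 | Vital-sign thresholds | Fisher |
| 8.2.4.3 to 8.2.4.6 | Tier 1 categories | None |

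Section 8.1.5 already uses a Cox hazard ratio with interval for time to first urinary retention or surgery. The times to first Tier 1 event are plotted without one.

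**3. How common can a pooled category be without triggering a comparison?** If a category has k terms, each below 5%, its pooled rate is below k x 5%. Term counts are from Appendix 8, Table A:

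- Impotence: 4 terms, so up to 20%
- Altered libido: 5 terms, so up to 25%
- Ejaculation disorders: 10 terms, so up to 50%
- Breast disorders: 11 terms, so up to 55%

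These are ceilings, not expected rates. They show that no pooled rate as such triggers a comparison.

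**4. What the missing interval would look like.** The counts and arm sizes here are assumptions. The interval is Newcombe's, built from Wilson limits (l, u) for each arm, with d = p1 - p2:

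lower = d - sqrt[(p1 - l1)^2 + (u2 - p2)^2]; upper = d + sqrt[(u1 - p1)^2 + (p2 - l2)^2]

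*Pooled category, 45/300 versus 24/300.* p1 = 0.150 (Wilson 0.1140 to 0.1948), p2 = 0.080 (0.0543 to 0.1163), d = 0.070.
- Lower = 0.070 - sqrt(0.0360^2 + 0.0363^2) = 0.019
- Upper = 0.070 + sqrt(0.0448^2 + 0.0257^2) = 0.122
- Fisher p = 0.010

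*Rare category, 6/300 versus 1/300.* p1 = 0.0200 (0.0092 to 0.0429), p2 = 0.0033 (0.0006 to 0.0186), d = 0.0167.
- Lower = 0.0167 - sqrt(0.0108^2 + 0.0153^2) = -0.002
- Upper = 0.0167 + sqrt(0.0229^2 + 0.0027^2) = 0.040
- Fisher p = 0.123

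The same formula at about the same rates and other arm sizes:

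| Counts | Difference | 95% interval | Fisher p |
|---|---|---|---|
| 22/150 v 12/150 | 6.7% | -0.6% to 14.0% | 0.10 |
| 45/300 v 24/300 | 7.0% | 1.9% to 12.2% | 0.010 |
| 90/600 v 48/600 | 7.0% | 3.4% to 10.6% | 0.0002 |

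The by-arm percentages give nearly the same difference in all three rows. Only the interval separates an excess that could be nil from one that is clearly present.

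**The case against.** **Sources not shown.** Section 8.2 and Appendix 5 rely on a Program Safety Analysis Plan, and Appendix 16 keeps the table shells in separate documents. Either could hold a Tier 1 comparison. This stands as a limit on certainty. It does not remove the point, because the RAP writes out its Tier 2 test and estimate in full and names nothing comparable for Tier 1.

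**Part of the information is there.** A reader might infer that the plan cannot say how large any excess is, or that no Tier 1 event is ever compared. The documents support neither. A crude difference follows from the by-arm percentages. A single Tier 1 term that reaches 5% is compared as Tier 2. Breast examination shifts and the six overall AE sets are tested, and Figure 3.2 plots the power to detect a difference in AE rates. None of these gives an interval for a pooled or rare Tier 1 category.

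**The pooled example is demanding.** With 300 per arm, below 5% means at most 14 subjects per term, so 45 subjects need at least four terms (45/14 = 3.2), nearly all at that ceiling. This is strained for libido, with five terms, and less so for ejaculation, with ten. If one term dominates, Tier 2 picks it up. That is fair, and the point does not rest on the example.

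**Descriptive reporting is a legitimate choice.** It is, and the primary inference is untouched. But the choice fits poorly with a tier defined by predefined hypotheses, and the plan does not state it.

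**Conclusion.** The point holds in this form: the RAP text specifies no between-arm effect estimate, interval or test for any pooled Tier 1 category, while Tier 2 terms selected by frequency get all three. What is lost is the reported uncertainty of the excess, chiefly for multi-term and rare categories. Its size in this trial cannot be stated, since the illustrations rest on assumed counts and arm sizes.

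Calling the tiers inverted would go too far. The Tier 2 analysis contains no identified error and needs no change; the gap is on the Tier 1 side. The change should be made, but it affects safety reporting only and no efficacy conclusion. The verdict assumes that the unseen safety plan and shells add no Tier 1 comparison. If they do, the RAP should say so.

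**What to change.** In 8.2.4.3 to 8.2.4.6, for each Tier 1 category, add the between-arm risk difference (or odds ratio) with a 95% score-type interval, exact where data are sparse, labelled as unadjusted for multiplicity. The categories are:

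- the four sexual and breast categories and the two breast subgroups
- prostate cancer
- the six cardiovascular categories and their total
- the twelve infrequent categories in 8.2.4.6

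That is 4 + 2 + 1 + 7 + 12 = 26 estimates. State what is shown when an arm, or both arms, have no events.

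Where events are sufficient, by a minimum count fixed before unblinding, add a Cox hazard ratio with interval beside the Kaplan-Meier curves already planned. Leave Tier 2 as it is.

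**Cost.** No new data are needed, only RAP wording, added columns in existing safety tables and some programming. Section 9 repeats all planned outputs for each of four countries, so the additions recur there, often with very few events. The price is a larger set of unadjusted safety estimates, which must be labelled and read as such.

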8.2.4.3. Sexual and Breast Tier 1 Adverse Events of Special Interest

Altered (decreased) libido, impotence, ejaculation disorders, and breast disorders, will be defined as sexual and breast adverse events of special interest. In addition, two subgroups of breast disorders (breast disorders: breast enlargement, and breast disorders: breast tenderness) are of special interest. MedDRA system organ class and preferred terms included in these special interest adverse events are defined in [Appendix 8, Table A](#).

Total number of, as well as number and percentage of the subjects experiencing, sexual and breast adverse events of special interest will be provided by treatment group. In addition, for each of the events of special interest, the number and percentage of subjects by treatment will be provided for the following:

- having an event
- having multiple events
- having an event in 6-month windows, starting from treatment start date

The following categories are related to the occurrence of the first event of the special interest AE; number and percentage of subjects in these categories will be provided by treatment group:

- drug-related AE
- serious AE
- AE leading to withdrawal from the study
- AE leading to permanent discontinuation of study drug
- AE outcome
- AE resolution status (on-therapy vs. off-therapy – see [Appendix 8](#) for definition)
- AE maximum intensity

The number and percentage of the subjects experiencing an adverse event of special interest will be provided by treatment group for the following. The by-baseline summaries will be output in the above described overall tabular summaries:

- By baseline age group: < 65 years, ≥65 years
- By sexual activity at baseline (Yes, No) based on “sexually active” question.

The number and percentage of subjects experiencing the following types of sexual and breast adverse events of special interest will be provided by treatment group:

- Any Type (Impotence, Decreased Libido, Ejaculation Disorders, or Breast Disorders)
- One AE Type
- Two AE Types
- Three AE Types
- All Four AE Types

The time to first onset in days will be summarized by treatment group as a continuous variable as well as by time period of onset. In addition, time to first adverse event of special interest will be summarized by treatment group using estimates calculated by the Kaplan-Meier method and displayed graphically as Kaplan-Meier curves. Time to resolution for the first event in days will be summarized by treatment group.

Duration of adverse events of special interest will be summarized by treatment group for uncensored values, censored values, and all values. It is recognized that summary statistics such as means and medians involving censored values will be biased (low).

The number of sexual and breast adverse events leading to study withdrawal, as well as the number and percentage of subjects reporting at least one such sexual and breast adverse event will be provided for all event types and also by event type for each treatment group.

Resolution status at end of study (resolved, not resolved) and time from treatment stop date to AE resolution will be summarized by treatment group for the sexual and breast adverse events leading to study withdrawal and not resolved at Month 24 / End of Treatment visit.

Listings of sexual and breast adverse events of special interest will be provided. A listing of sexual and breast adverse event status data will be provided.

A listing of the TFUQ data for sexual and breast adverse events will be provided.

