The number of post-randomization adverse events, the number and the percentage of subjects reporting any post-randomization AE will be summarized by treatment group for the following:

- All AEs
- Drug-related AEs
- Serious AEs
- AEs leading to study drug discontinuation
- AEs leading to withdrawal from study
- Fatal AEs

Comparisons of treatment groups for each of these sets of AEs will be performed using Fisher's Exact Test.

Total number of adverse events reported in the study as well as the number and percentage of subjects reporting at least one AE will be provided for each treatment group. Total number of AEs as well as the number and percentage of subjects reporting each AE will be reported by treatment group, primary system organ class and preferred term. On-treatment and post-treatment AEs will be summarized separately, as well as together as post-randomization AEs. Non-serious post-randomization AEs will be summarized by treatment group. A summary of post-randomization AEs will be provided by treatment group and six month time period of onset (Months 1-6, Months 7-12, Months 13-18, Months 19-24), by treatment group and age group (<65 years, \geq 65 years), by treatment group and age group (<75 years, \geq 75 years), and by treatment group and country.

A summary of post-randomization AEs will be provided by treatment group and preferred term by descending frequency of preferred term (regardless of system organ class). In addition, such summaries will be done for serious post-randomization AEs and also for non-serious post-randomization AEs.

For on-treatment AEs, the event rate per 100 person-years of study drug exposure will be summarized by treatment group, primary system organ class and preferred term overall and by time period (Months 1-6, Months 7-12, Months 13-18, Months 19-24).

A summary of post-randomization AEs will also be provided by treatment group and maximum intensity. If the same AE occurs on multiple occasions in the same subject, the AE with the highest intensity will be presented. Intensity will be categorized as mild, moderate, or severe; a category for missing/not applicable intensity will be included.

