8.2.4.4. Prostate Cancer Tier 1 Adverse Events of Special Interest

Prostate cancer will be defined as an adverse event of special interest. MedDRA preferred terms and codes included in this special interest adverse event are defined in [Appendix 8, Table B](#). Prostate cancer events will be summarized separately following the same format done for sexual and breast special interest AEs described above. Time to first event for prostate cancer events will be summarized separately by treatment group using estimates calculated by the Kaplan-Meier method and displayed graphically as Kaplan-Meier curves.

Listings of prostate cancer adverse events of special interest will be provided.

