8.2.4.6. Infrequent Tier 1 Adverse Events of Special Interest

Infrequent Tier 1 adverse events of special interest will be defined as those included in the following categories:

- Breast cancer
- Potential for decreased male fertility due to effects on sperm/semen characteristics
- Interference with formation of external genitalia in a male fetus if a woman carrying a male fetus is exposed to dutasteride

- Hair changes
- Allergic reactions
- Depressed mood
- Testicular pain and swelling
- Intraoperative floppy iris syndrome
- Orthostasis
- Priapism
- Stevens-Johnson syndrome
- Atrial fibrillation, tachycardia, arrhythmias

MedDRA preferred terms and codes included in these special interest adverse events are defined in [Appendix 8, Table D](#). Total number of infrequent Tier 1 events as well as the number and percentage of subjects with infrequent Tier 1 events will be provided by treatment group.

Listings of infrequent Tier 1 adverse events of special interest will be provided.

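### Special-interest adverse event tables for sexual/breast, prostate cancer and cardiovascular categories describe each subject by his first event, so category counts of serious, fatal, severe or treatment-ending events can be understated

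*SAP*

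**What the plan says.** SAP section 8.2.4.2 defines Tier 1 events as terms for which "there are predefined hypotheses about the existence of a potential treatment effect". It names four groups: sexual and breast, prostate cancer, cardiovascular, and infrequent events.

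For sexual and breast events, section 8.2.4.3 first asks for subjects with an event, with multiple events, and with an event in each 6-month window. It then introduces a second list with "The following categories are related to the occurrence of the first event of the special interest AE". That list holds seven items: drug-related, serious, leading to study withdrawal, "AE leading to permanent discontinuation of study drug", outcome, resolution status (on or off therapy) and maximum intensity.

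The format is reused. Section 8.2.4.4: "Prostate cancer events will be summarized separately following the same format done for sexual and breast special interest AEs described above". Section 8.2.4.5 applies it to each of six cardiovascular categories and to "all cardiovascular events as one additional category, will be summarized separately following the same format done for sexual and breast special interest AEs". By Table 5 of the SAP (amendment 01 numbering), the affected displays are Tables 3.42-3.47, 3.54 and 3.56-3.62.

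For the infrequent group, section 8.2.4.6 asks for counts alone: "Total number of infrequent Tier 1 events as well as the number and percentage of subjects with infrequent Tier 1 events will be provided".

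**The concern.** The plan expects repeat events, since it tabulates men with more than one. For those men, the first event is a poor guide to the worst one. An event that is fatal, or that makes a man stop the drug or leave the study, tends to be his last in the category, so among men with repeats the rule works against counting it.

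These rows describe the risks that the plan itself singles out. A reader who asks how many men in each arm had a serious cardiovascular event, or stopped the drug because of an ejaculation disorder, would look here and could read a number that is too low. If recurrence differs between arms, the shortfall differs too and the comparison is affected. The documents do not say in which direction.

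**Working it through.** No figure in the plan depends on this rule, so there is nothing to reproduce. The check is a counting identity followed by a reading of the related sections.

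**1. Direction and bound.** For one category and one yes/no attribute, let F be the subjects whose first event has the attribute, A the subjects with at least one event that has it, and L the subjects whose first event lacks it but a later one has it. Then

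A = F + L, so F ≤ A.

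Every subject in L has at least two events in the category. So the shortfall A − F = L cannot exceed the number in the multiple-events row of the same table. It is zero where no one has a repeat.

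**2. Where it bites.** Appendix 8, Table C puts milder and graver terms into one category:
- Acute Coronary Syndrome: unstable angina together with myocardial infarction and cardiac death.
- Ischemic Cerebrovascular Events: transient ischemic attack together with cerebral infarction.
- Cardiac Arrhythmias: ventricular extrasystoles together with ventricular fibrillation.

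A man who moves from the first-named kind of event to the second is described by the first.

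The pooled Table 3.62 is more exposed, because a first event in any of the six categories fixes the attributes. Take a non-serious ventricular extrasystole followed by a fatal myocardial infarction. In Table 3.56 the infarction is the man's first acute coronary event and appears with its own seriousness and outcome. In Table 3.62 he carries those of the extrasystole.

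For a sexual category, take mild decreased libido that resolves, then a recurrence that makes the man stop the drug. Table 3.42 shows him as mild, resolved and not leading to discontinuation.

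**3. How the plan treats repeats elsewhere.**
- General intensity table (section 8.2.2): "If the same AE occurs on multiple occasions in the same subject, the AE with the highest intensity will be presented".
- Duration (Appendix 8): adds up days over all of a subject's events and is censored if any contributing event is censored. The man with recurrent libido loss could be shown as resolved while his duration is censored by an ongoing recurrence.
- Study withdrawal, sexual and breast events (section 8.2.4.3, Tables 3.49-3.53): subjects with at least one such event, overall and by type. This can differ from the first-event withdrawal row for the same category.

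**4. Can the category count be recovered from other tables?** Section 8.2.3 summarizes serious and fatal events, and section 8.2.4.1 those leading to withdrawal or discontinuation, with no first-event limit. Subject counts by preferred term do not add up to a category count, because one man may report several terms; Acute Coronary Syndrome alone has nine. Peripheral Vascular Disease is an exception, since it has a single term. Otherwise no planned table gives, by prostate cancer or cardiovascular category, the subjects with at least one serious, fatal or treatment-ending event. None gives at-least-one serious or drug-discontinuation counts by sexual or breast category.

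**The case against.** The strongest reply is that the rule is explicit, prespecified and coherent with time to first onset and time to resolution of the first event, which sit in the same tables. No tests are planned on these rows, and the multiple-events row keeps recurrence visible. All of that stands. It supports keeping the first event for timing; it does not make the first event the right basis for seriousness, outcome or discontinuation.

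Several stronger readings are tempting and are not supported:
- A reader might infer that all special-interest events are affected. The infrequent Tier 1 group is outside the rule, because section 8.2.4.6 asks only for event and subject counts and does not adopt the format.
- A reader might infer that later grave events are lost from the report. They are not: they appear in the general tables (3.25-3.40), in Listings 3.5-3.8 and in Listing 3.12. They are absent only from the category attribute rows.
- A reader might infer that withdrawal due to sexual or breast events is counted only from first events. Tables 3.49-3.53 count it on an at-least-one basis.
- A reader might infer that section 8.2.2 contradicts section 8.2.4.3. Its highest-intensity rule covers intensity only, for the same adverse event, in another table. This is a difference of convention.
- A reader might attach a percentage to the shortfall. That needs the share of men with repeats and the chance that an event is serious, and the plan gives neither. One assumed range would also have to cover conditions as unlike as libido loss, prostate cancer and stroke.

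**Conclusion.** The concern holds in a limited form. In Tables 3.42-3.47, 3.54 and 3.56-3.62, counts of subjects with a related, serious, fatal-outcome, severe or treatment-ending event in a category can be understated, and can never be overstated. The effect is clearest in categories that mix milder and graver terms and in the pooled cardiovascular Table 3.62. The direction follows from the counting rule without assumptions. The size is unknown before the data are seen and is bounded by the number of men with repeat events in the category. This is a weakness in how safety is presented; it does not bear on the efficacy conclusions.

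**What to change.** In sections 8.2.4.3 to 8.2.4.5 and Tables 3.42-3.47, 3.54 and 3.56-3.62:
- Count a subject as drug-related, serious, leading to study withdrawal or leading to permanent discontinuation if any post-randomization event in the category has that attribute.
- Show the worst outcome and the maximum intensity over all events in the category.
- Keep the first-event basis for time to first onset, resolution status and time to resolution of the first event, and label those rows accordingly.

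Table 3.55 is the MedDRA-term summary and needs no change. The data are already collected. The cost is a wording change, minor reprogramming of the affected tables and their shells, and slightly less favourable counts.
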